The current IMDs guidelines are cautious about the recommendations on the use of CGM and its clinical practice application in nutritional improvements or modifications (15–17). Rossi et al. have recently proposed indications for CGM monitoring and CGM outcome parameters in patients with hepatic GSDs (14). Peeks et al. also indicated outcome parameters for hepatic GSDs (13).

Worth et al. have recently analyzed the state of art of the evidence for the use of CGM in non-diabetic children with hypoglycemia (9). Some suggestions for qualified CGM use have been provided, but a focus on patients' perspectives on the use of different CGM systems is still lacking, especially on recent tools developed by new technologies.

Study Objectives

Primary objective

Assessment of Pre-set targeted time in hypoglycemia and number of episodes of pre-set hypoglycemia during the different periods of use of CGM tools based on different alarms.

Secondary objectives

Accuracy of the two different CGM systems (comparator SBGM by capillary finger stick).

Assessment of patients' perspectives and tolerance to the use of two subsequent different CGM systems and tools, in particular on different types of alarms: Dexcom One Plus (Dexcom) with threshold alarm and Dexcom G7 (Dexcom) with predictive alarm.

Assessment of quality of life and sleep quality.

Assessment and comparison of glycemic control, patients' perspective and tolerance of CGM with USUAL Care CGM.

Study Design

Study Type

Prospective interventional with medical devices CE

Study Site

Sample Size Estimation

11 IMDs at risk for hypoglycemia

The rare condition of disorders investigated needs to be considered for the sample size (e.g. GSD I has a frequency of approximately 1 in 100,000 and the estimated incidence of CHI ranges between 1:27,000 and 1:50,000 live births in outbred western population).

Randomization

Patients will be randomized to start with the use of Dexcom G7 o Dexcom One Plus after baseline.

Methods for randomization: Randomization will be employed to assign participants to different

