Continuous Glucose Monitoring (CGM) systems to ensure unbiased comparisons across the study groups. Simple randomization using computer-generated random numbers will be implemented to allocate patients randomly. This method will help distribute confounding variables evenly between groups, thereby minimizing selection bias. Block randomization may also be utilized to maintain balance in the number of participants among the groups throughout the study. Allocation concealment will be maintained until the intervention assignment to prevent any potential influence on patient enrollment.

Statistical method

Definition of Analysis Sets

The following data sets will be analyzed:

- Full analysis set (FAS):
The set of subjects is as close as possible to the ideal implied by the intention-to-treat principle. All subjects with at least one efficacy follow-up will be included. It is derived from the set of all eligible subjects by minimal and justified elimination of subjects. When handling of missing values of primary outcomes, the last observation carried forward (LOCF) method will be applied.
- Per-protocol analysis set (PPS):
The per protocol analysis set will consist of all patients in the full analysis set plus the following criteria: completion the treatment process, without any major protocol violations, good compliance (80%~120% medical device and capillary finger sticks compliance) and without missing value in primary outcomes. Patients with at least one major protocol violation (e.g missing the 8 weeks efficacy follow up) will be excluded from the per-protocol analysis.
- Safety Set (SS):
The safety set will consist of all subjects followed at least one period with one CGM system.

Endpoints:

Primary: number of episodes of pre-set hypoglycemia (hypoglycemia <70 mg/dL and severe hypoglycemia < 54 mg/dL), time above, under or in pre-set target range, glycemic variations during the different periods of use of CGM tools based on different alarms;

Secondary objectives

Secondary: accuracy and MARD (comparator finger capillary sticks) during the use of two different CGM; perspectives and preferences in monitoring and specific use of different alarms with Dexcom One Plus or with Dexcom G7; correlation of primary endpoint with the quality of sleep, quality of life and/or neurocognitive outcomes i.e. attention, assessed by specific questionnaires; perspectives and preferences in monitoring and specific use of different CGM with Usual Care monitoring.

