Statistical Analysis (example)

(1) General Principles

Quantitative variable will be described by the total number of cases, number of missing values, mean, and standard deviation, minimum, maximum and median. Categorical variables will be described by the number of cases and percentages.

All statistical tests will be performed using two-sided test, P value less than or equal to 0.05 will be considered to have examined the difference statistically significant (Unless otherwise noted). For comparison between two groups of the general condition, the suitable method shall be adopted to conduct analysis according to the type of indicators; for the comparison among groups of quantitative data, group t test (homogeneity of variance, normal distribution) or Wilcoxon rank-sum test will be adopted according to the data distribution (the Shapiro-Wilk test will be used beforehand to check whether the variables follow a normal distribution or not); for categorical data, the chi-square test or Fisher's exact test (if the chi-square test is not applicable) shall be adopted; for ordered data, Wilcoxon rank-sum test or Cochran-Mantel-Hansel test shall be adopted. Multiple regression analyses will also be considered, including linear regression for continuous dependent variables, Poisson regression and cumulative logit logistic regression for ordered response variables (or logistic regression for dichotomous variables, such as presence/absence). Moreover, ANOVA or mixed-effects models will be used to compare how the effect of interest varies over time within the same subject, repeated measures.

(2) Completion and Baseline Parameters

The summary of the study completion includes the count of completed cases of each study center, the list of dropout cases, the analysis set description, the comparison of dropout rates of the groups and the list of reasons for incompleteness. The summary of baseline parameters includes demographic characteristics (gender, age, height, vital signs etc.), history of illness and medications, and specific Questionnaires about CGM tolerance, perspectives and expectations. Comparisons among the two different CGM devices groups and gold standard by capillary finger stick will be conducted to evaluate MARD and reliability during the period of observation.

(3) Compliance

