Quality of Life Evaluation: SF-12 Rating Scale		x	x	x
Specific Questionnaires for CGM Tolerance, Perspectives, and Expectations		x	x	x
Quality of Sleep: Pittsburgh Sleep Quality Index (PSQI)		x	x	x
Education on the use of CGM device		x	x	x

Study Population

Inclusion Criteria

Adult patients with Glycogen Storage Disease (GSD) or Congenital Hyperinsulinism (CH), aged over 18 years, who have had at least one clinical and biochemical follow-up at the hospital outpatient service within the last year or two years. This includes patients with a biochemical or genetic diagnosis of GSD or CH.

Exclusion Criteria

Inability to sign consent or comply with study procedures. No additional conditions are expected that could introduce bias in the results and therefore require further exclusion criteria.

Study Evaluation

The Ethics Committee of every study site will guarantee the safety of the subjects, receive the effective data and conduct the review on process analysis, and ensure that this study is conducted as per the highest standard of ethics.

Study Quality Control

This study will be conducted by trained and qualified investigators. The investigators shall fill in the CRF in a trustful, detailed and earnest manner to ensure that the content included in the CRF is complete, authentic and reliable. During the study process, the study institution shall conduct examination against case report forms randomly.

Requirements of Ethics

This study complies with the Declaration of Helsinki (version 2000) strictly, and will be conducted as per the relevant medical research regulations and provisions in Italian country.

Before the subjects are included in this study, the investigators are responsible for introducing the purposes, procedures and potential risks of this study to the subjects and their guardians in a complete and comprehensive manner in writing. The subjects have the right to withdraw from this study at any time. Prior to the commencement, it is essential to receive the written informed consent of each subject, which shall be reserved for filing as a clinical research document.

Management Principles

Resume

The latest resume of each investigator and collaborator shall be submitted to the study institution prior to the commencement of this study.

Record Storage in the Study Site

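### The secondary correlations with sleep, quality of life and attention are not fixed in number and fall under an unadjusted 0.05 rule, so the chance of a false finding exceeds 5% by an amount that depends on the reading

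*Combined protocol and SAP*

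**What the plan says.** Under Endpoints, the secondary list includes the "correlation of primary endpoint with the quality of sleep, quality of life and/or neurocognitive outcomes i.e. attention, assessed by specific questionnaires". The primary endpoint named there is several things: "number of episodes of pre-set hypoglycemia (hypoglycemia <70 mg/dL and severe hypoglycemia < 54 mg/dL"), time above, below and within the target range, and glycemic variation, all across the periods of device use. Counting each separately gives six measures.

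The flowchart in the Observation parameters list schedules the PSQI and the SF-12 at baseline and after each 30-day device period. It names no instrument for attention.

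Under Statistical Analysis (example), General Principles, the rule is: "All statistical tests will be performed using two-sided test", and a "P value less than or equal to 0.05 will be considered to have examined the difference statistically significant". An exception is allowed where otherwise noted, but none is noted for these correlations. The plan names no correlation coefficient, gives no testing order or adjustment, and calls no secondary analysis exploratory. The sample is "11 IMDs at risk for hypoglycemia", justified by rarity alone.

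**The concern.** The endpoint reads as one correlation but opens onto a family of unknown size. The primary side is a list, the other side is two or three domains joined by and/or, and both sides are measured in two device periods. The analyst can settle which pairs to compute and report after seeing the data, and the only decision rule in the plan calls each of them significant at 0.05.

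At stake is how the results on sleep and quality of life are read. The protocol names both among its secondary objectives. In a sample of 11, any correlation that passes the threshold is numerically large, so a chance finding would look like a strong association between glycemia and how patients sleep or feel.

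**Working it through.** **The plan's own figure.** The documents give the sample size of 11 but no effect size, standard deviation, power, number of tests or family-wise error. There is nothing to reproduce, and the number of tests has to be assumed.

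**Inputs from the documents.** Two-sided 0.05 per test (General Principles); n = 11 (Sample Size Estimation); two device periods and two questionnaires (Observation parameters list).

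**Counts of measures.**
- Two, if only the primary objective is used: time in hypoglycemia and number of episodes.
- Five, if the CRF list of CGM values is used with both episode thresholds: two episode counts and three times.
- Six, if the Endpoints section is used, which adds glycemic variation.

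**Counts of scores.** Two, with one score per questionnaire, or three, with two summary scores for the SF-12. The documents do not say how the questionnaires are scored, so both counts are assumptions. Attention is left out of the counts below.

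**Critical correlation.** With n − 2 = 9 degrees of freedom, t = 2.262, and |r| = 2.262 / √(9 + 2.262²) = 0.602. Power at a true correlation of 0.5 is about 34%.

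**Independent tests.** With k tests and no true association, the chance of at least one false positive is 1 − 0.95^k. This gives 9.75% for k = 2, 18.5% for 4, 46.0% for 12, 48.7% for 13, 51.2% for 14, 64.2% for 20 and 84.2% for 36. Under independence it passes one half only from 14 tests.

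**Dependent tests.** Independence overstates the risk: the three times sum to 100%, and episodes follow time below range. I therefore simulated 20,000 trials per setting, with n = 11, Pearson tests, measures unrelated to scores, and an assumed common correlation within each set of variables. Where both periods are tested, the between-period correlation is assumed to be 0.6. The last column is 0.05k.

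| Reading | Tests | Within-set 0 | 0.5 | 0.8 | Expected false positives |
|---|---|---|---|---|---|
| 2 measures × 2 scores, one period | 4 | 18.5% | 17% | 12% | 0.2 |
| 6 × 2, one period | 12 | 46% | 37% | 22% | 0.6 |
| 6 × 3, one period | 18 | 60% | 47% | 28% | 0.9 |
| 5 × 2, both periods | 20 | 63% | 54% | 36% | 1.0 |
| 6 × 2, both periods | 24 | 70% | 58% | 39% | 1.2 |
| 6 × 3, both periods | 36 | 83% | 71% | 46% | 1.8 |

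One measure against three scores in one period gives 13% at a within-set correlation of 0.5.

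**Structured check.** I also let time in range be fixed by the times above and below, and let episodes follow time below. With 6 × 2 the result is 35% for one period and 53% to 56% for both. With 5 × 2 it is 30% for one period and 47% to 51% for both. The two-period ranges cover between-period correlations of 0.6 to 0.8.

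**The case against.** The strongest reply is that this is mostly labelling. The analyses are already ranked secondary, the diseases are rare, the sample is 11, and the analysis section is headed as an example. The text speaks of the primary endpoint in the singular, names no correlation test, and words its threshold for a difference. The plan also mentions mixed-effects models for repeated measures, so separate correlations in each period are not stated. All of this stands as a limit on what can be claimed. It does not remove the point, because the rule's subject is all statistical tests and nothing exempts these.

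Four stronger readings are tempting and are not supported:
- **A false positive is more likely than not.** This holds only in the larger families. At a within-set correlation of 0.5, every one-period reading above is below one half, and at 0.8 even 36 tests give 46%.
- **Every primary measure will be crossed with every score and each result judged.** The text does not say so. It leaves the pairs open.
- **One or two significant associations are to be expected by chance.** That fits families of about 18 to 36 tests. Four tests give 0.2 and twelve give 0.6.
- **The small sample inflates the false-positive rate.** A valid test keeps its 5% at any n. Small n only makes whatever passes look large.

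Nor would such a correlation show that alarms affect sleep, since it relates glucose measures to questionnaire scores and not to alarm type. Finally, the device comparison of the primary measures has its own multiplicity question, and the same general rule drives both. The hypotheses differ, however, and settling the primary comparison alone would leave the 0.05 rule on these correlations.

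**Conclusion.** The point holds in a limited form. The correlation endpoint fixes neither its pairs nor its method, and the plan's only decision rule is an unadjusted 0.05. With no true association, the chance of at least one significant correlation exceeds 5% in every reading with more than one pair, short of perfect dependence. It runs from about 17% (2 × 2, one period) through 37% (6 × 2, one period) and 54% (5 CRF-listed measures × 2, both periods) to 71% (6 × 3, both periods).

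These figures assume a within-set correlation of 0.5, a between-period correlation of 0.6, Pearson tests, and no true association anywhere. The correlations and the numbers of tests are my assumptions, not the plan's. The chance exceeds one half mainly when both periods are tested separately and the measures are not strongly correlated. Any significant result would show a correlation of at least 0.60 in absolute value.

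**What to change.** Under Endpoints, label the correlation endpoint exploratory and state that all prespecified correlations will be reported as estimates with 95% confidence intervals and without significance statements. Prespecifying them means listing the measures, scores and periods to be paired before the data are examined. Under General Principles, state that the 0.05 rule does not apply to these correlations.

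The interval conveys what a significance label hides. For r = 0.602 and n = 11, Fisher's transformation gives z = 0.696 with standard error 1/√8 = 0.354. The limits are 0.696 ± 1.96 × 0.354 = 0.003 and 1.389, which correspond to correlations of about 0.00 and 0.88.

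The label and the exemption take a sentence each, plus the list of pairs. No data or patients are added. The price is that no significance claim can be made for the associations with sleep and quality of life.

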- Compliance of study: study compliance to the CGM two medical devices and capillary finger sticks of all groups will be described and compared. A list of subjects with poor compliance (80% below or 120% above compliance) will be generated.

Observation parameters list (CRF)

Patients at screening, baseline, after 30 days of **unblinded monitoring** with Dexcom G7 and 30 days of **unblinded monitoring** with Dexcom One Plus (Fig. 2). The start of the single CGM tool will be randomized (i.e. 50% of patients will random start with G7 and then switch to Dexcom One Plus, and *viceversa*).

- 1) SCREENING _ General data collection: age, gender, height, body weight, minority, career, income, degree of education, family history, smoking habit, primary diseases or accompanied diseases.
- 2) SCREENING _ Previous glucose monitoring (referring to the last 8 weeks): number of capillary fingers sticks per day, use (or not) of CGM and type of CGM device
- 3) SCREENING _ Major comorbidities
- 4) SCREENING _ Document intake of medications
- 5) SCREENING _ Adverse events and the rate of hospitalization during the last year
- 6) BASELINE _ Quality of Life (SF-12 rating scale)
- 7) BASELINE _ Quality of Sleep (Pittsburgh sleep quality index (PSQI))
- 8) FOLLOW UP _ Capillary finger sticks glucose values (3 per day) by diary record

- 9) FOLLOW UP_ CGM values: time above, under or in the pre-set target, number of episodes of pre-set hypoglycemia
- 10) FOLLOW UP_ CGM tolerance, perspectives and expectations (Specific questionnaires)
- 11) FOLLOW UP_ CGM Quality of Sleep (Pittsburgh sleep quality index (PSQI), quality of life (SF12))
- 12) FOLLOW-UP_ Education on the use of CGM device (sensor, receiver or other tools)

Flowchart indicating which parameter is measured when:

Observation Parameters	Screening	Enrollment/Baseline	Follow up - After 30 days	Final Visit study - After 30 days
Informed consent	x			
Demographic (Age, Gender, Career, Degree of Education, Income)	x			
Height	x			
Body Weight	x	x	x	x
Family History	x			
Smoking Habit	x			
Physical exam	x			
Vital signs	x			
Primary Diseases or Accompanied Diseases	x			
Major IMD Comorbidities	x			
Glucometer values		x	x	x
Use of CGM	x			
Documented Intake of Medications	x			
Rate of Hospitalization During the Last Year	x			
Type of CGM Device	x	x	x	x
Capillary finger sticks glucose values (3 per day)		x	x	x
CGM values (time in pre-set hypoglycemia, number of pre-set hypoglycemia, MARD)		x	x	x

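### The plan names a p≤0.05 threshold but no between-device estimate with a 95% confidence interval; with 11 patients, a non-significant result could not exclude a moderate difference

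*Combined protocol and SAP*

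**What the plan says.** All of this is in the combined protocol and SAP.

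- **Statistical Analysis (example), (1) General Principles.** On description: "Quantitative variable will be described by the total number of cases, number of missing values, mean, and standard deviation, minimum, maximum and median". On inference: "All statistical tests will be performed using two-sided test", and "P value less than or equal to 0.05 will be considered to have examined the difference statistically significant". The threshold may be overridden where noted, but no other criterion is noted. For quantitative comparisons between groups, "group t test (homogeneity of variance, normal distribution) or Wilcoxon rank-sum test will be adopted according to the data distribution". Regression models are to be considered, and ANOVA or mixed-effects models are to be used for repeated measures within a subject. No device contrast, ratio or interval is attached to any of them.
- **Sample Size Estimation.** The number is "11 IMDs at risk for hypoglycemia", and the reason is that "The rare condition of disorders investigated needs to be considered for the sample size". No effect size, SD, power or precision is given.
- **Observation parameters list (CRF).** Each patient uses both devices for 30 days, in random order: "50% of patients will random start with G7 and then switch to Dexcom One Plus", and the reverse for the others.
- **Endpoints.** The primary endpoints are several: hypoglycemic episodes at two thresholds, time above, under and in range, and glycemic variation, compared across periods with different alarms.

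The plan states no equivalence margin, no smallest important difference, and no rule for interpreting p>0.05.

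**The concern.** The comparison of the two alarm types is the main result of this trial. Rarity fixes the number of patients, so the trial can improve only what it reports from them. A p-value above 0.05 in 11 patients fits two situations: the devices hardly differ, or they differ and the trial is too small to show it. A device effect with its interval separates the two, because it shows which differences the data exclude.

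The planned per-device means and SDs do not fill the gap. The variance of a within-patient difference is s₁² + s₂² − 2ρs₁s₂, and the plan does not ask for ρ, the correlation between a patient's two periods. A reader given two means, two SDs and a p-value can subtract the means but cannot obtain the paired interval from the two SDs.

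**Working it through.** **The plan's own figure.** N = 11 cannot be reproduced, because the plan gives no effect size, SD, correlation, power or dropout rate. The check therefore asks what 11 patients can deliver.

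**Inputs.** From the documents: n = 11, two-sided α = 0.05, two periods per patient, nominally equal sequences (5 and 6 at best). Assumed: approximately normal within-patient differences, effects expressed in units of their SD, and 0.5 SD taken as moderate.

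**Power.** Paired t test with 10 degrees of freedom, noncentrality d√11 = 3.317d, critical value 2.228.

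| True difference d (SD of within-patient difference) | Power |
|---|---|
| 0.3 | 14.7% |
| 0.5 | 32.3% |
| 0.8 | 66.8% |
| 0.94 | 80% |
| 1.0 | 84.8% |

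With a period term and a 5/6 split (9 degrees of freedom), power at 0.5 SD is 31.5%, and 80% is reached at 0.95 SD. Reaching 80% power at 0.5 SD with a paired test would take 34 patients.

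**Half-width of the 95% interval.**

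- Paired, n = 11: t(0.975, 10)/√11 = 2.228/3.317 = 0.672 SD.
- Period-adjusted, 5/6: t(0.975, 9) × ½√(1/5 + 1/6) = 2.262 × 0.3028 = 0.685 SD.
- Paired with fewer complete patients: 0.715 SD for 10, 0.769 for 9, 0.836 for 8.

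**What a non-significant result leaves open.** In units of the observed SD, the paired interval is 2 × 0.672 = 1.344 wide. If p>0.05 it contains zero, so it must reach at least 0.672 from zero on one side or the other. A difference of 0.5 SD in at least one direction is then always left open.

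A simulation of 200,000 trials with a true difference of 0.5 SD gave p>0.05 in 67.5% of them. In 96.3% of those, the interval still contained 0.5 SD.

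**Dependence on scale.** If the effect is instead 0.5 of the between-patient SD, it equals 0.5/√(2(1−ρ)) on the scale above, and the answer turns on ρ:

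| ρ | Power | Half-width, between-patient SD: 0.672 × √(2(1−ρ)) |
|---|---|---|
| 0 | 18.6% | 0.950 |
| 0.5 | 32.3% | 0.672 |
| 0.7 | 49.0% | 0.521 |
| 0.8 | 65.7% | 0.425 |
| 0.9 | 91.5% | 0.301 |

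The documents give no value for ρ.

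**The case against.** The strongest reply is that the plan offers more than a p-value.

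- **Estimates are available.** Means and medians are planned for every quantitative variable, and with complete data the difference between the two device means is a point estimate. The mixed models and regressions could also yield effects with intervals. This stands to the extent that a reader who infers that no estimate is planned goes too far. What is missing is a pre-specified device contrast with its interval. The models name no contrast, and what software happens to print is not a planned result.
- **No false conclusion is written down.** A reader might infer that a non-significant result will be reported or read as equal efficacy. The documents do not say so: they claim no equivalence and are silent on p>0.05. The plan leaves that misreading open but does not commit to it.
- **The threshold is a general convention.** It applies to all tests, under a heading marked as an example, and the primary objective is worded as an assessment with no hypothesis attached. This is fair, but no other inferential criterion appears.
- **Large effects would usually be found.** A reader might infer that significance is unlikely even if one alarm clearly helps. The figures do not support that: power is 67% at 0.8 SD and 85% at 1.0 SD. The shortfall concerns small and moderate effects.
- **The scale matters.** With a within-patient correlation near 0.9, an effect of 0.5 of the between-patient SD would usually be detected. This stands, but the correlation is unstated, and an interval would show the precision actually reached.
- **One mean difference would not suit every endpoint.** This is correct: episodes are counts, and there are two periods to adjust for. It shapes the fix below.

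**Conclusion.** The point holds as an inexpensive improvement to the analysis plan. It does not make the trial invalid. The plan specifies a significance threshold and per-variable summaries, but no between-device effect with a 95% interval. At n = 11, a paired analysis has about 32% power at 0.5 SD of the within-patient difference and needs about 0.94 SD for 80%. Its interval half-width is about 0.67 SD (0.685 with a period term and a 5/6 split, wider with dropout), so p>0.05 could not exclude a moderate difference.

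These figures assume a paired analysis, roughly normal differences, complete data, and 0.5 SD of the within-patient difference as moderate. They apply to the continuous endpoints. Precision for a rate ratio of episodes depends on event counts and their variability, which the documents do not give.

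**What to change.** In General Principles, add wording such as:

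> For each primary endpoint, the device comparison will be reported as the within-patient, period-adjusted G7 versus One Plus effect with its 95% confidence interval: a difference for time-in-range and variability measures, a rate ratio for episode counts. A p-value above 0.05 will not be interpreted as absence of a difference.

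In Sample Size Estimation, keep the rarity argument and add the precision it buys for the continuous endpoints. The expected 95% half-width is about 0.67 SD of the within-patient difference, or 0.685 SD with a period term and a 5/6 split; it widens if patients do not complete both periods.

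The cost is slightly more analysis work, since a model must be named for each type of endpoint, and an interval that will be openly wide. No extra patients or data are needed.

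### The plan lists both independent-group and within-patient methods for a two-period crossover, does not say which gives the G7 v One Plus contrast, and names no period term

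*Combined protocol and SAP*

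**What the plan says.** **Design.** Observation parameters list (CRF) gives each patient 30 days on G7 and "30 days of unblinded monitoring with Dexcom One Plus". The order is randomized: "50% of patients will random start with G7 and then switch to Dexcom One Plus", and the rest do the reverse. The primary endpoints (Endpoints) are compared across the periods of use of the two tools. Sample Size Estimation gives "11 IMDs at risk for hypoglycemia", supported only by rarity: "The rare condition of disorders investigated needs to be considered for the sample size". Randomization specifies simple randomization, with blocking as an option.

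**Analysis.** Statistical Analysis (1) General Principles sets the level: "All statistical tests will be performed using two-sided test, P value less than or equal to 0.05". For comparisons among groups of quantitative data, "group t test (homogeneity of variance, normal distribution) or Wilcoxon rank-sum test will be adopted according to the data distribution". Categorical data go to chi-square or Fisher's exact test, and ordered data to rank-sum or a Cochran-Mantel-Haenszel type test. No paired t, signed-rank or McNemar test is named. The paragraph ends by saying that "ANOVA or mixed-effects models will be used to compare how the effect of interest varies over time within the same subject". Section (2) Completion and Baseline Parameters then says "Comparisons among the two different CGM devices groups and gold standard by capillary finger stick will be conducted".

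**The concern.** The group t, rank-sum, chi-square and Fisher tests, applied to one set of values per device, assume different people in the two sets. Here they are the same 11 people. The plan's own phrase, which makes the devices into groups, invites that use.

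Three things are at stake. First, an analyst could follow the section faithfully with either family of methods and reach different standard errors and p-values, and could choose between them after seeing the data. Second, if the independent-group family is chosen, between-patient variance stays in the error term. That gives up the main advantage of a crossover in a trial whose size is fixed by rarity. Third, period 2 follows a month of unblinded monitoring, with education scheduled again at later visits, so a change between periods unrelated to the device is plausible. With 11 patients the two sequences cannot be equal, so an analysis without a period term mixes part of that change into the device effect.

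**Working it through.** **Inputs from the documents:** n = 11, two periods per patient, two-sided 0.05, simple randomization to sequence. **Assumed, because the documents give none:** outcome SD of 1 in each period, within-patient correlation rho from 0 to 0.8, and the size of any period effect. The figure of 11 cannot be reproduced, because no effect size, SD, correlation or power is stated.

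**Step 1. Standard error of the device difference (SD units).**
- Independent groups: sqrt(2/11) = 0.426, whatever rho is.
- Paired: sqrt(2(1-rho)/11).
- Period-adjusted crossover at 6:5: sqrt[(2(1-rho)/4) x (1/6 + 1/5)], almost identical to paired.
- Ratio of independent to paired: 1/sqrt(1-rho).

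**Step 2. Consequence.** Group t test results are simulated with no period effect. Crossover power is from the noncentral t with 9 df. Power is for a true difference of 0.6 SD.

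| rho | Paired SE | SE ratio | Group t, true type I error | Group t, power | Period-adjusted, power |
|---|---|---|---|---|---|
| 0 | 0.426 | 1.00 | 5.1% | 27% | 24% |
| 0.3 | 0.357 | 1.20 | 2.3% | 24% | 32% |
| 0.5 | 0.302 | 1.41 | 0.9% | 21% | 42% |
| 0.7 | 0.234 | 1.83 | 0.2% | 17% | 63% |
| 0.8 | 0.191 | 2.24 | 0.05% | 15% | 80% |

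Simulated power is good to about one percentage point. For positive rho the group test rejects too rarely.

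**Step 3. Period effect.** Let delta be the G7 minus One Plus difference and pi the period 2 minus period 1 effect. A patient starting on G7 has expected difference delta - pi; a patient starting on One Plus has delta + pi. With n1 and n2 patients in the two sequences, the unadjusted mean difference is delta - pi(n1 - n2)/11. The fraction of pi that leaks is:
- 6:5: 1/11 = 9%
- 7:4: 3/11 = 27%
- 8:3: 5/11 = 45%

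Under simple randomization, the probability of 8:3 or worse is 2 x (1 + 11 + 55 + 165)/2048 = 464/2048 = 22.7%.

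**Step 4. Is pairing alone enough?** With rho 0.7 and an assumed period effect of 0.5 SD, a plain paired t test has type I error 2.4% at 6:5 and 8.6% at 8:3. The period-adjusted test stays at about 5% in both.

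**The case against.** A reader might infer that the plan will analyse the device contrast with independent-group tests, so that its standard error is certainly wrong and no period effect is removed. The documents do not support that. The group tests are no more assigned to the device contrast than the mixed models are. Their sentence opens with the general condition of the two groups, which can be read as baseline characteristics. The within-subject sentence is a commitment in the same paragraph and fits an endpoint compared across periods at least as well. Leaving period unnamed is not the same as excluding it. This part of the objection stands, and the finding is conditional for that reason.

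A two-sample t or rank-sum test is also valid when it compares within-patient period differences between the two sequences. That is correct, but the plan does not say that the tests are applied to such differences.

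The loss depends on an unstated rho. At 0.3 it is modest (24% against 32%), and at 0 the group test is slightly ahead (27% against 24%). That stands too. At 6:5 the leak is small: 0.5/11, about 0.05 SD, for a 0.5 SD period effect. A period effect is plausible but unquantified. Some patients may already use CGM, and the time-design figure is not visible in the text available to me, so I make no claim about washout.

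Finally, one might read the trial as a parallel comparison of 6 against 5 patients. The CRF section rules this out, because every patient switches device.

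What the objection does not remove is that the plan speaks of device groups, names no paired test, and ties no model or period term to its primary comparison.

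**Conclusion.** The concern holds in conditional form. The plan leaves its main comparison open between two families of methods, one of which does not fit the design if applied to the values by device, and it specifies no period or sequence term for either. If the group tests are used on the device contrast, the standard error is inflated by 20% at rho 0.3 and by 124% at rho 0.8, and power at 0.6 SD falls short of the period-adjusted analysis by about 8 to 65 percentage points over that range. The direction is conservative for any positive rho. The risk is a missed difference, or an interval too wide to use, rather than a false claim. Separately, an analysis without a period term, even a paired one, is biased by 1/11 to 5/11 of any period effect for splits from 6:5 to 8:3, and more for worse splits.

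These sizes rest on assumed values of rho and of the period effect. The mismatch between design and listed tests, and the missing period term, rest on the text alone. Because the point governs the primary comparison and is settled by wording, it should be fixed before the data are analysed.

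**What to change.** In Statistical Analysis (1) General Principles, and wherever the devices are called groups:

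1. State that all G7 v One Plus comparisons are within-patient.
2. For continuous primary endpoints (time in, above and below range; glycemic variation), use a linear mixed model on one value per patient per period, with fixed effects for device and period and a random patient effect.
3. For episode numbers, use the count analogue, for example a Poisson or negative binomial mixed model with the same terms and log wear time as offset.
4. Report the device effect with its 95% confidence interval.
5. Use paired methods for binary and ordinal questionnaire items.
6. Restrict the two-sample t and rank-sum tests to baseline comparison of the two sequences, or to within-patient period differences compared between sequences. The rank-sum form of the latter can serve as the non-parametric back-up.

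The cost is SAP wording: no new data and no extra patients. Period takes one degree of freedom (9 instead of 10 for the simple continuous analysis). If rho were near 0, power would be about 3 percentage points lower than with the group t test (24% against 27% at 0.6 SD).
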